**Table 5.2 Summary of statistical analyses**

Outcome	Indicator	Timing	Statistical Analysis
Primary outcome			
Neonatal mortality	Death during 1 st 28 days of life	2 and 6 week visits, clinic record abstraction	Log-binomial regression
Secondary outcomes			
Early neonatal mortality	Death during 1 st 7 days of life	2 and 6 week visits, clinic record abstraction	Log-binomial regression
Initiation of early breastfeeding	Breastfeeding in 1 st hour of life	2 week visit	Log-binomial regression
Exclusive breastfeeding	Cessation of EBF in 1 st 6 weeks of life	2 and 6 week visits	Cox proportional hazards
Thermal care	Bath in 1 st 24 hours of life	2 week visit	Log-binomial regression
Cord care	No application of substances to cord	2 week visit	Log-binomial regression
Home provision of KMC	Any duration of skin-to-skin care on ≥10 of the first 14 days at home, among low birthweight or preterm infants	2 and 6 week visits	Log-binomial regression
Maternal knowledge of neonatal danger signs	Number of the 8 danger signs or symptoms successfully named	2 and 6 week visits	Poisson GEE
Appropriate care seeking	Proportion of illness episodes with danger signs where the infant attended the clinic and/or where the infant was hospitalized regardless of danger signs reported in study follow-up	2 and 6 week visits, ongoing record abstraction	Log-binomial regression
Depression	Score above diagnostic threshold (≥13) for Edinburgh Postnatal Depression Scale	Baseline, 2 and 6 week visits	Log-binomial GEE
Social support	Score using MOS Social Support Survey	Enrollment, 2 and 6 week visits	Linear GEE
Self-efficacy	Score using Self-efficacy in Infant Care Scale	Baseline, 2 and 6 week visits	Linear GEE

**Notes:**

1. *if any log-binomial regressions fail to converge, Poisson regression with robust standard errors will be used for all comparisons of proportions.*
2. *If data needs to be imputed, the exclusive breastfeeding analysis will be conducted using Poisson regression with time offset instead of Cox regression, as this is asymptotically equivalent and easier to implement.*

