#### a. Analyses based on survival analysis

Assuming alpha=0.05, 2-sided test, 1:1 allocation ratio, with a sample size of 2,500 per arm, and 10% attrition, we will have  $\geq 80\%$  power to detect a Hazard Ratio (HR) of 0.53 in neonatal mortality, assuming mortality of 23 per 1000 births in the control arm. Assuming alpha=0.0045 (Bonferroni-adjusted for 11 tests) and 2-sided test, we will have  $\geq 80\%$  power to detect a difference of 90.0% vs. 93.1% continued exclusive breastfeeding to 6 weeks.

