### 5.3 Analysis of study endpoints

1. **Neonatal mortality.** Among live-born infants, the proportion who die in the first 28 days postpartum will be compared between arms by log-binomial regression. As a *secondary analysis* of this outcome, a Bayesian analysis will be conducted using Markov Chain Monte Carlo modeling to estimate the probability that the Mobile WACh NEO treatment effect exceeds a range of potential values. Models with a range of prior probabilities will be developed.
2. **Early neonatal mortality.** Among live-born infants, the proportion who die in the first 7 days postpartum will be compared between arms by log-binomial regression.
3. **Initiation of early breastfeeding.** Proportion of infants who initiate breastfeeding in the first hour of life will be compared between arms by log-binomial regression.
4. **Cessation of exclusive breastfeeding.** Time to first introduction of complementary foods will be compared between arms by Cox proportional hazards regression.
5. **Bath.** Proportion of infants who are bathed in the first 24 hours of life will be compared between arms by log-binomial regression.
6. **Application of substances to cord.** Proportion of infants who have any substance applied to their cord will be compared between arms by log-binomial regression.
7. **Maternal provision of Kangaroo Mother Care (KMC).** Among women whose babies were born at <37 weeks gestation or weighing <2500g, proportion of who provide KMC on  $\geq 10$  of the first 14 days that the baby is home will be compared by log-binomial regression.
8. **Maternal knowledge of neonatal danger signs.** The mean number of 8 neonatal danger signs correctly named by mothers at the 2-week and 6-week visits will be compared between arms by Poisson generalized estimating equations (GEE). Exploratory analyses will evaluate time-dependent effects by incorporating timepoint as an interaction term.
9. **Appropriate care seeking.** The proportion of illness episodes with danger signs where the infant attended the clinic and/or where the infant was hospitalized independent of neonatal danger signs in the first 18 weeks of life (study follow-up period). Illness episodes are based on maternal self-report and only include the most recent illness episode at the 6-week visit, or 2-week visit if data is unavailable at the 6-week visit. Differences in proportions will be compared between arms by log-binomial regression.

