# Compared by linear GEE

#### **5.4 MISSING DATA**

Based on the Mobile WACh NEO pilot, we expect 10% loss to follow-up between enrollment and the 6-week study visit. We anticipate that dyads who are lost to follow-up are more likely to be disengaged from care and have experienced adverse outcomes. We also anticipate missingness may differ by arm, with the intervention arm having higher retention. Sensitivity analyses will be conducted for the primary mortality outcome assuming all missing participants did or did not experience neonatal mortality. If missing data rates were unexpectedly appreciably higher than these rates, more nuanced sensitivity analyses would be considered, such as those that consider differing rates of neonatal mortality for the missing participants that differ by arm. Variables with >10% missingness will be multiply imputed by MICE.

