Appropriate care-seeking outcome definition & analysis	20 April 2023	3.3	
 
Proportion of illness episodes with danger signs in which infant attended the clinic and/or infant was hospitalized independent of neonatal danger signs in the first 6 weeks of life Analyzed by log-binomial GEE
 
	
 
Proportion of illness episodes with danger signs in which infant attended the clinic and/or infant was hospitalized independent of neonatal danger signs during the study period (up to 18 weeks). If data is unavailable at the 6-week visit, data from the 2-week visit will be used. Analyzed by log-binomial regression
 
	Data collection error resulted in care-seeking only being collected for the most recent illness episode. 6-week visits could occur up to 18 weeks postpartum and we elected to include all data reported at study visits, regardless of when the care-seeking event occurred.
Approach to missing data	14 August 2023	3.4	Sensitivity analyses	Variables with >10% missingness will be imputed by multiple imputation by chained equations (MICE).	Two outcomes and one adjustment variable were found to have high levels of missingness. Multiple imputation has been shown to lead to less biased results than complete case analysis, and allows preservation of sample size.

Approach to exclusive breastfeeding cessation analysis	11 December 2023	3.5	Cox regression	For data imputed by MICE, use Poisson regression with time offset	Implementation of Cox regression with imputed data was unclear and Poisson regression is asymptotically equivalent.
Use of log-binomial vs Poisson regression	11 December 2023	3.5	Log-binomial regression	If any log-binomial regressions fail to converge, we will instead use Poisson regression with robust standard error	Log-binomial regressions frequently fail to converge. Poisson regression with robust standard errors yields asymptotic results.

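### The SAP calls Poisson regression with a time offset asymptotically equivalent to Cox; as described that holds in general only under a constant hazard, though the likely error is small

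*SAP*

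**What the plan says.** SAP section 5.3, item 4, gives the planned analysis: "Time to first introduction of complementary foods will be compared between arms by Cox proportional hazards regression". Note 2 under Table 5.2 replaces it, when data need to be imputed, with "Poisson regression with time offset instead of Cox regression, as this is asymptotically equivalent and easier to implement". The entry in Table 6.1 dated 11 December 2023 (version 3.5) gives the reason: "Implementation of Cox regression with imputed data was unclear and Poisson regression is asymptotically equivalent". Neither place mentions splitting follow-up time, a term per interval, a constant hazard or a robust variance. Note 1's robust standard errors cover comparisons of proportions only.

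The trigger for imputation is in the SAP section on missing data: "Variables with >10% missingness will be multiply imputed by MICE". The same section says "We also anticipate missingness may differ by arm, with the intervention arm having higher retention". The Table 6.1 entry of 14 August 2023 reports that "Two outcomes and one adjustment variable were found to have high levels of missingness", without naming them.

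**The concern.** Cox regression leaves the baseline hazard free. A Poisson model whose only time element is a person-time offset compares events per unit of person-time and assumes one constant baseline rate. The two converge to the same ratio in general only if that rate really is constant, or if follow-up is cut finely and each interval has its own term. The second is a different model from the one described.

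Nothing in the documents supports a constant rate of stopping exclusive breastfeeding over the first 6 weeks. If the rate changes with age and the arms contribute different lengths of follow-up, length of follow-up becomes mixed with arm. The SAP itself expects retention to differ by arm. At stake is the effect estimate for one secondary endpoint.

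**Working it through.** **1. The plan's own figure.** SAP section 3a gives "1:1 allocation ratio, with a sample size of 2,500 per arm, and 10% attrition" and, for breastfeeding, "Assuming alpha=0.0045 (Bonferroni-adjusted for 11 tests) and 2-sided test", with at least 80% power for 90.0% vs 93.1% still exclusively breastfeeding at 6 weeks.

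- Evaluable per arm: 2,500 × 0.90 = 2,250. Events: 2,250 × (0.100 + 0.069) = 380.
- HR = ln(0.931)/ln(0.900) = 0.679, so |ln HR| = 0.388.
- Schoenfeld power: Φ(0.388 × √380/2 − 2.841) = Φ(0.94) = 82.6%. The Freedman formula gives 81.4% and a two-proportion test 81.6%.
- Minimum detectable proportion: 93.03% to 93.06%.

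The stated figure reproduces. The second scenario in Table 3.1, 80.0% vs 84.2%, implies HR = 0.771.

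**2. What the Poisson model estimates.** Assume proportional hazards with a Weibull baseline: S(t) = exp{−H(t/6)^k}, t in weeks. In control, H = −ln(0.900) or −ln(0.800); in the SMS arm, H is multiplied by the HR. k = 1 is a constant hazard, k < 1 a falling one, k > 1 a rising one. The range of k is an assumption.

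The large-sample rate ratio is (E1/P1)/(E0/P0), where E is the expected proportion stopping and P the expected weeks at risk (the integral of S over follow-up). Cox estimates the HR itself.

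**3. Equal follow-up to 6 weeks.** Example with k = 0.5 in the first scenario: (0.069/5.7215)/(0.100/5.5948) = 0.675 against 0.679, or −0.6%.

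| k | HR 0.679: Poisson limit (error) | HR 0.771: Poisson limit (error) |
|---|---|---|
| 0.3 | 0.672 (−0.9%) | 0.760 (−1.4%) |
| 0.5 | 0.675 (−0.6%) | 0.764 (−0.9%) |
| 1 | 0.679 (0) | 0.771 (0) |
| 2 | 0.682 (+0.6%) | 0.777 (+0.9%) |
| 3 | 0.684 (+0.9%) | 0.781 (+1.3%) |

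With HR = 1 both arms have the same E and P, so the limit is 1.00 at every k. Simulation at 2,250 per arm (300 runs) agrees: 0.675 for Poisson vs 0.679 for Cox at k = 0.5, and 0.684 vs 0.680 at k = 2. Poisson power stayed near 80% to 83%.

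**4. Follow-up that still differs by arm.** Suppose a fraction m is lost at 2 weeks and stays censored there, so E and P are weighted averages over follow-up of 2 and 6 weeks. The fractions are assumptions. Example with 20% control and 10% SMS loss, k = 0.5, HR = 1, 10% stopping: (0.0959/5.2273)/(0.0918/4.8599) = 0.971.

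| Loss, control vs SMS | HR = 1: limit for k = 0.5 to 3 | HR = 0.679: error for k = 0.5 to 3 |
|---|---|---|
| 10% vs 5% | 0.987 to 1.017 | −1.9% to +2.6% |
| 15% vs 5% | 0.973 to 1.037 | −3.3% to +4.6% |
| 20% vs 10% | 0.971 to 1.040 | −3.4% to +4.9% |

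A falling hazard pushes the ratio down and a rising hazard pushes it up. At k = 1 the error is zero throughout.

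**5. Time after 6 weeks.** Table 6.1 says the 6-week visit could be as late as 18 weeks. As an illustration only, let 20% of control and 10% of SMS visits fall at 12 weeks with all that time counted, and HR = 1. The limit is 1.05 (k = 0.5), 0.90 (k = 2) or 0.81 (k = 3). The last two carry a rising hazard out to 12 weeks. Censoring at 6 weeks, as the endpoint definition implies, removes the effect.

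**6. Standard errors.** With equal follow-up, no effect and nominal alpha 0.0045, model-based errors rejected at 0.0058 (k = 0.3) to 0.0032 (k = 3) with 10% stopping, and at about 0.007 to 0.003 with 20%. Robust errors gave 0.0041 to 0.0051 (Monte Carlo error about 0.0005 to 0.0008).

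**The case against.** A reader might infer that, because the SMS arm is expected to be better retained, the switch biases the result toward benefit by several percent. With stopping concentrated in the first weeks (weekly hazard shares 6:3:2:1:1:1 or 10:2:1:1:1:1, cumulative hazard 0.223, so about 20% stopped by 6 weeks) and no true effect, the ratio is 0.98–0.99 for losses of 12% vs 8%, 0.95–0.96 for 20% vs 10% and 0.93–0.95 for 25% vs 10%. The documents do not support that reading:

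- These figures leave lost infants censored at day 14 and impute nothing, whereas note 2 applies only to imputed data. If event and time are both imputed to 6 weeks within arm, the ratio is 1.00 in every one of these settings.
- The SAP expects 10% loss. Only the 12% vs 8% case averages to that.
- The hazard shape is assumed, and a rising hazard reverses the direction.
- It is not stated that breastfeeding was one of the two outcomes with high missingness. A rule written for it four months later makes that plausible, no more.

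Two further defences have some force. A time offset is also used in an interval-split Poisson model, so part of the problem may be under-specification; but no split is described, and the one-offset reading is the natural one. The SAP also does not say that Cox results cannot be pooled, only that implementation was unclear and Poisson easier. Nor is the switch hidden, since Table 6.1 records it, and the Table 5.3 shell has no column for an effect ratio.

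What survives is that the equivalence is stated without its condition. The SAP does not say whether event, time or both are imputed, or to what horizon, so equal follow-up after imputation cannot be taken for granted.

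**Conclusion.** The equivalence claim is wrong as written, and the consequence is probably small. Under the SAP's own scenarios with equal follow-up to 6 weeks, the error is under 1% of the hazard ratio for 90.0% vs 93.1% and under 1.5% for 80.0% vs 84.2%, even at Weibull shapes of 0.3 and 3. It vanishes when there is no effect. If imputation leaves person-time unequal between arms, an error of a few percent in either direction is possible; counting time after 6 weeks could add more if the hazard rises. These sizes rest on assumed hazard shapes and assumed losses by arm. The point concerns one secondary endpoint, only when data are imputed. It does not touch the mortality analysis and does not show a bias in favour of the intervention.

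**What to change.** Delete the statement of asymptotic equivalence from note 2 and from the justification in Table 6.1. Then choose one of:

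- Fit Cox in each imputed data set and pool the log hazard ratios by Rubin's rules. This keeps the planned model.
- Use Poisson regression with follow-up split by week (or day), a term for each interval and robust standard errors. This approaches Cox as the intervals become fine.

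Under either option, state that event and time are imputed together and that follow-up is censored at 6 weeks. If the Poisson option is kept, change the footnote to Table 5.3, which still names Cox for this endpoint. The cost is a few lines of code and some SAP wording, with no new data.

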**Table 5.3 Study endpoints: shell table**

	Overall	Control	SMS	p-value
Aim 1				
* Neonatal mortality (per 1000 live births)				
Aim 2				
* Early neonatal mortality (per 1000 live births)				
\$ Time to introduction of complementary food				
* Breastfeeding initiated within 1 hour (%)				
* Bathed within 24 hours (%)				
* Substances applied to cord (%)				
* Provision of KMC among LBW/PTB infants (%)				
^ Number of danger signs identified				
+ Proportion of illness episodes with danger signs or hospitalization				
Aim 3				
+ Elevated depressive symptoms (%)				
# Social support score				
# Parenting self-efficacy score				

\* Compared by log-binomial regression

\$ Compared by Cox proportional hazards regression

\* Compared by log-binomial regression

^ Compared by Poisson GEE

+ Compared by log-binomial GEE

[figure not shown]
# Compared by linear GEE

#### **5.4 MISSING DATA**

Based on the Mobile WACh NEO pilot, we expect 10% loss to follow-up between enrollment and the 6-week study visit. We anticipate that dyads who are lost to follow-up are more likely to be disengaged from care and have experienced adverse outcomes. We also anticipate missingness may differ by arm, with the intervention arm having higher retention. Sensitivity analyses will be conducted for the primary mortality outcome assuming all missing participants did or did not experience neonatal mortality. If missing data rates were unexpectedly appreciably higher than these rates, more nuanced sensitivity analyses would be considered, such as those that consider differing rates of neonatal mortality for the missing participants that differ by arm. Variables with >10% missingness will be multiply imputed by MICE.

## 5.4 INTERIM ANALYSIS

An interim analysis for neonatal mortality will be performed using O'Brien-Fleming boundaries for benefit and harm when 50% of expected person time has been accrued. The plot below shows the standardized z-value boundaries for interim monitoring.

## 5.5 SAFETY MONITORING

Adverse and severe adverse events, including social harms such as violence or breach of confidentiality, will be monitored, and unblinded results will be reviewed by the DSMB. The DSMB will make recommendations regarding any imbalances in safety outcomes.

**Table 5.4 Adverse and severe adverse events: shell table**

SAE #	PTIDNO	SAE description	Severity (Grade)	Onset date	Duration (days / unresolved)	Onset since randomization (days)	Relatedness to study

## 6. MODIFICATIONS TO ANALYSIS PLAN

Table 6.1 records modifications made to the analysis plan and their justification. Note changes made after December 2022 were after our final DSMB meeting and were not approved by the DSMB.

**Table 6.1. Summary of modifications**

Description of modification	Date of modification	Modified SAP version	Original approach	Updated approach	Justification
Outcome definition	8 October 2020	2.4		
 
Added early neonatal mortality as secondary outcome
 
Added KMC as secondary outcome
 
	DSMB recommendation
Mortality analysis approach	8 October 2020	2.4	Cox proportional hazards	
 
Log-binomial regression
 
Secondary Bayesian approach
 
	DSMB recommendation
Missing data approach	8 October 2020	2.4	None specified	Added approach	DSMB recommendation
Appropriate care-seeking outcome definition & analysis	23 December 2022	3.0	
 
Number of illness episodes where care was sought or baby was hospitalized
 
Analyzed by Poisson regression
 
	
 
Proportion of illness episodes with danger signs in which infant attended the clinic and/or infant was hospitalized independent of neonatal danger signs in the first 6 weeks of life
 
Analyzed by log-binomial GEE
 
	Data collection error resulted in care-seeking only being collected for the most recent illness episode.
Depression outcome definition	23 December 2022	3.0	Depression threshold cut-off listed as both 12 and 13	Clarified that cut-off was $\geq 13$	An EPDS score of 13 is a commonly used cut-off in the literature and was specified in clinicaltrials.gov

Social support outcome definition	23 December 2022	3.0	Range of social support score values not specified	Clarified that this outcome will use the transformed mean scale (possible values 0-100) per the validated measure	
Parental self-efficacy outcome definition	23 December 2022	3.0	Range of self-efficacy score values not specified	Clarified that this outcome will use the summed score scale (possible values 0-45) per the validated measure. Also specified that score will only include 10 questions in original validated score; custom questions will be analyzed in exploratory analysis.	
Knowledge of neonatal danger signs outcome definition	31 January 2023	3.0	Definition specified 7 neonatal danger signs, unclear which ones were used	Definition now specifies 8 neonatal danger signs 
 
● Difficulty feeding
 
● Weakness
 
● Hypothermia
 
● Fever
 
● Fast breathing
 
● Difficulty in breathing
 
● Convulsions
 
● Yellowness
 
	Messages in intervention group discussed these 8 neonatal danger signs but did not mention the 9 th sign listed in the CRF (sign of umbilical cord infection)
Education cut-off value	31 January 2023	3.0	Completed primary education used as cut-off	Completed secondary education used as cut-off	Given the high percentage of participants who completed primary education (>90%), this cut-off allows more discrimination comparing education between study arms
Intended pregnancy	6 February 2023	3.0	Compared proportion of pregnancies that were intended between arms	Will not include this variable in Table 1	Due to an error in skipping patterns, this question was not asked of primigravida individuals. Therefore, the data is not useful for comparing arms.

Use of intention-to-treat analysis	27 March 2023	3.2	Use intention-to-treat analysis on primary outcomes	Adjust for reported SMS messages from other programs in primary analysis Add secondary per-protocol analysis excluding individuals who reported receiving SMS messages from other programs	During the study, the study team became aware of other SMS health messaging interventions operating in the study area. This change to statistical analysis will adjust for contamination to the intervention by other SMS programs.
Other SMS messages	27 March 2023	3.2		Added receipt of SMS messages from another program to Table 1	This addition will describe how many individuals received SMS messages from other programs by arm.
Appropriate care-seeking outcome definition & analysis	20 April 2023	3.3	
 
Proportion of illness episodes with danger signs in which infant attended the clinic and/or infant was hospitalized independent of neonatal danger signs in the first 6 weeks of life Analyzed by log-binomial GEE
 
	
 
Proportion of illness episodes with danger signs in which infant attended the clinic and/or infant was hospitalized independent of neonatal danger signs during the study period (up to 18 weeks). If data is unavailable at the 6-week visit, data from the 2-week visit will be used. Analyzed by log-binomial regression
 
	Data collection error resulted in care-seeking only being collected for the most recent illness episode. 6-week visits could occur up to 18 weeks postpartum and we elected to include all data reported at study visits, regardless of when the care-seeking event occurred.
Approach to missing data	14 August 2023	3.4	Sensitivity analyses	Variables with >10% missingness will be imputed by multiple imputation by chained equations (MICE).	Two outcomes and one adjustment variable were found to have high levels of missingness. Multiple imputation has been shown to lead to less biased results than complete case analysis, and allows preservation of sample size.

Approach to exclusive breastfeeding cessation analysis	11 December 2023	3.5	Cox regression	For data imputed by MICE, use Poisson regression with time offset	Implementation of Cox regression with imputed data was unclear and Poisson regression is asymptotically equivalent.
Use of log-binomial vs Poisson regression	11 December 2023	3.5	Log-binomial regression	If any log-binomial regressions fail to converge, we will instead use Poisson regression with robust standard error	Log-binomial regressions frequently fail to converge. Poisson regression with robust standard errors yields asymptotic results.
